10.1 Adverse Event Reporting

MAD treatment for mild to moderate OSAH has been used extensively in clinical trials and in patient populations. Thus its adverse event profile is generally well known. Description of the tolerability and adverse event profile is an important aim of this trial. It is unlikely that novel (unexpected) adverse events will occur and the adverse event profile is anticipated to be modest.

An adverse event (AE) is defined as 'any untoward occurrence in a participant or clinical investigation subject receiving a trial intervention and which does not necessarily have a causal relationship with this intervention'. An AE can therefore be any unfavourable or unintended sign (including an abnormal laboratory finding), symptom or disease temporally associated with the use of the study intervention, whether or not considered related to the intervention.

Adverse Reactions (AR)

An **AR** is an AE where a causal relationship with the intervention is at least a reasonable possibility i.e., the relationship cannot be ruled out.

Expected Adverse Reactions

MAD therapy is generally very well tolerated. The main expected ARs of MAD therapy are:

Temporomandibular joint / Jaw Discomfort Mouth Discomfort Dry Mouth Excessive Salivation Gum Discomfort Tooth Discomfort Loose Teeth Malocclusion

These ARs can be minimised by careful MAD fitting. The frequency of these ARs will be recorded on the case report forms (CRFs).

Unexpected Adverse Reactions

Mouth ulcers

An Unexpected AR is one which is of a nature or severity that is not consistent with the expected AR profile of the trial intervention. Unexpected ARs will be recorded on the CRFs. The probability of Unexpected ARs is low.

Recording of Adverse Events

For this trial, the AE reporting period is from randomisation to the patient's last trial visit (after the 4th treatment), or until the point of patient withdrawal from the trial. AE recording will be limited to any ARs, any other AE considered by the Principal Investigator to be of medical interest/importance to the trial and all Serious AEs (SAEs – see Section 10.2). AEs will be recorded on the routine CRFs.

It will be left to the investigator's clinical judgement whether or not an AE is of sufficient severity to require the patient's removal from the trial treatment. A patient may also voluntarily withdraw from treatment if they find an AE to be intolerable.

The secondary adverse consequences of sleepiness (the correction of which is the primary reason for considering MAD therapy in OSAHS) are recorded as trial outcomes.

Severity of Adverse Events

The severity of AEs will be graded as mild, moderate or severe.

Relationship to trial treatment

The relationship between the trial treatment and the AE (the causality) will be graded as: Unrelated, Possibly related, Definitely related.

Follow-up after Adverse Events

All AEs will be followed up until resolution or to the end of the AE reporting period.

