Eligible Participants: Participants will be given and asked to complete a sleep diary each morning over the 6 weeks treatment period or 4 weeks no period treatment to assess sleep duration, snoring, compliance and retention. The participant will be asked to return the diary when they attend for the outcome measures at the end of each treatment.

Manufacture of MADs: An appointment will be made for participants to attend Addenbrooke's Hospital Oral-Maxillofacial department. Participants will first be assessed to confirm suitability for inclusion into the trial by [name], consultant maxillofacial surgeon, a consultant colleague or a trained and supervised delegate. If suitable then they will be measured and return for fitting of the bespoke MAD (see below).

In order to manufacture the semi-bespoke Sleep Pro 2 device participants will be given an impression kit to take home to mould and wear before sending it to the manufacturer in a pre-paid envelope (See Experimental Interventions below).

Experimental Interventions: Three broadly different types of MAD of varying sophistication, which represent devices currently available along a spectrum of complexity and cost, will be studied:

- 1) Sleep Pro 1 (SP1) (*Meditas Ltd., Winchester, UK*): A thermoplastic 'boil and bite' device which is fitted by the participant following the manufacturer's printed instructions. The participant softens the device in hot water then places it into their mouth and, having bitten down on it, advances the mandible to an individually-determined 'comfortable' position. The device is then manually moulded against the teeth and sets by subsequent immersion in cold water. Rewarming allows remoulding. (http://www.sleeppro.com).

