- 2) Sleep Pro 2 (SP2) (*Meditas Ltd., Winchester, UK*): A semi-bespoke device, formed from a dental impression mould used by the participant. An impression kit is posted to the participant. It consists of a SP1 with holes to allow the injection of dental putty, and the putty ingredients. The participant is instructed to mould the SP1 as above, then wear it for two nights to ensure optimum position and fit, remoulding if necessary. The participant then makes up the putty and injects it into the SP1, sending the resulting impression back to the manufacturer. The SP2 is produced from this mould. It is designed to grip the entire dentition. Thinner walls than the SP1 are intended to result in a more comfortable fit. Involvement of the participant's dentist in taking the impression is suggested, but it is not presented by the manufacturer as essential, nor key to achieving the best fit (http://www.sleeppro.com).
- 3) Bespoke Device (bMAD) (Oral-Maxillofacial laboratory, Cambridge, UK): Custom made MAD, professionally fitted by specialist NHS Oral-Maxillofacial laboratory at Addenbrooke's Hospital. A 'wax bite' will be taken from the participant, which is when the degree of mandibular advancement is determined. Determining the degree of advancement is a balance between advancing the mandible sufficiently to bring the tongue base off the posterior pharyngeal wall and maintaining participant comfort. An impression is made from the wax bite which will ultimately be translated into an acrylic MAD. The participant returns for the fitting of the acrylic MAD which allows for optimal participant comfort.

Degree of Protrusion

As this is a pragmatic trial the SP1 and SP2 devices will both be advanced by the patient, according to manufacturer's instructions. The bMAD will be fitted by qualified dental experts, who will determine the degree of protrusion with the patient, aiming for maximal comfortable advancement. The aim is to advance the mandible by a minimum of 50% of maximal protrusion. The degree of protrusion of each device will be measured by the trial team (RF), although this may be less accurate with the SP1.

VISITS 3 and 4

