Participants will attend Addenbrooke's Oral-Maxillofacial Laboratory for the measurement of the bespoke MAD approximately 1-2 weeks after their baseline visit with fitting 2 weeks later. Each appointment will take 20 minutes. In order to ensure devices are not used until the designated treatment period the bespoke MAD will be sent directly to the study team at Papworth Hospital.

Randomisation

Eligible participants who have given informed consent and satisfy all inclusion/exclusion criteria will go forward to the randomised trial. All participants will have a 6 week period of treatment in each of the 3 treatment arms and 4 weeks in the no treatment control arm. Randomisation will take place once eligibility has been confirmed following measurement for the bMAD and Meditas have confirmed that the impression sent by the participant is adequate to make the SP2 device. The trial team will contact Papworth R&D Department on [name] to receive the randomisation sequence which will be generated by the trial statistician. Further details on the randomisation strategy is included in Section 7.

The first treatment period will begin within four weeks of randomisation.

Intervention schedule: Following the manufacture of the MADs, participants will start the first treatment arm. All participants will receive each MAD for a period of 6 weeks (or no treatment control for 4 weeks) in a randomised order. The MAD will be posted to the participant a few days before the start of the treatment period (or letter advising of no treatment according to participant's intervention schedule) and will be asked to start using the device immediately. Participants will also be asked to complete the daily sleep diary.

The first 2 weeks of each treatment period will act as an acclimatisation phase to give participants time to adjust to each device and will not be considered part of active treatment. The no treatment control period will last 4 weeks.

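### Adverse-event recording opens at randomisation, after participants have already worn a study-supplied SP1-type impression mould for two nights, so reactions to that wear have no AE recording route

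*Protocol*

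**What the plan says.** **Recording window.** Protocol section 10.1: "For this trial, the AE reporting period is from randomisation". It closes at the final visit, following the fourth treatment, or at withdrawal if that comes first. The same section states that "Description of the tolerability and adverse event profile is an important aim of this trial".

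**Impression step.** Under the manufacture of the devices in section 3.4, "participants will be given an impression kit to take home to mould and wear before sending it to the manufacturer". The SP2 entry under the experimental interventions describes the kit: "It consists of a SP1 with holes to allow the injection of dental putty". The participant moulds it in the same way as the SP1, and is told to "wear it for two nights to ensure optimum position and fit, remoulding if necessary", before adding the putty and posting the result.

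**Timing of randomisation.** The randomisation paragraph of section 3.4 places it after measurement for the bespoke device and once "Meditas have confirmed that the impression sent by the participant is adequate to make the SP2 device".

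**Other records.** Section 3.3 keeps a screening log with reasons for non-inclusion. Section 3.5 sends withdrawal details to a CRF and lets participants leave without giving a reason. Section 3.4 has calls to the support line documented. Table 5 schedules side effects and withdrawals from V5/6 onwards.

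**The concern.** The kit is not a dental tray held in the mouth for a few minutes. It is an SP1 body, moulded to the participant's own bite with the jaw advanced, and worn overnight. The reactions section 10.1 expects from a mandibular advancement device could occur on those nights, and for participants with no previous exposure to such treatment (an exclusion criterion) this is their first wear of one.

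At stake is the completeness of the safety description, which the protocol names as an important aim. A participant who has a reaction and continues to randomisation leaves no AE record of it, so severity, causality and follow-up are not documented. A participant who has a reaction and stops does not contribute to the tolerability results. If a serious event occurred, staff would find two sections that do not clearly agree on whether it must be reported.

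**Working it through.** The point rests on the order of events, so the main check sets the sections in time order.

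1. Consent, baseline questionnaires and sleep study: visits 1 and 2 (section 3.4).
2. Impression kit supplied, moulded, worn for two nights and returned (section 3.4, manufacture of MADs and SP2 entry). No participant is exempted.
3. Manufacturer accepts the impression; bespoke-device measurement done (section 3.4).
4. Randomisation (section 3.4). The participation number is assigned here (section 5.1).
5. AE reporting period opens (section 10.1).
6. First treatment period begins within four weeks of randomisation (section 3.4).
7. First tolerability call two weeks after a device is started; first scheduled side-effect record at V5/6 (section 3.4, Table 5).

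Step 2 lies wholly before step 5.

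**Does a reaction at step 2 count as an AE?** Section 10.1 defines an AE by its link in time to use of the intervention, whether or not the intervention caused it, and does not mention randomisation. The kit is described inside the SP2 entry of the experimental interventions. Jaw, mouth, gum and tooth discomfort are on the expected-reaction list. On a plain reading such an event meets the definition but falls outside the recording period.

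**Serious events.** Section 10.2 defines an SAE as an AE meeting listed criteria and requires all SAEs to go to the sponsor once the team is aware, with no start date. Section 10.1 names SAEs among the events recorded within its period, which starts at randomisation. The two can be read either way.

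**Size of the unrecorded exposure.**
- Per randomised participant: at least 2 nights; remoulding may add to this.
- Across 90 to 96 randomised (Study Synopsis): 90 × 2 = 180 to 96 × 2 = 192 participant-nights, plus the wear of anyone who stops at this step.
- Relative to scheduled device wear: each device is used for 6 weeks, 6 × 7 = 42 nights, and there are three devices, 3 × 42 = 126 nights. So 2/42 = 4.8% of one device period and 2/126 = 1.6% of all device wear.

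**Plan's own figure.** The sample size does not enter this point. It reproduces closely: ((1.960 + 0.842)/(1/3))² = 70.6, or 72.6 with the paired t-test, against the stated 72; and 72/0.80 = 90.

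**The case against.** The strongest case against has five parts.

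- **Drop-outs are recorded.** A reader might infer that people lost at the impression step disappear. The documents do not support that: the screening log covers all reasons for non-inclusion, and section 3.5 sends withdrawal details to a CRF without limiting it to randomised participants. This stands. What remains is that these are not AE records, that no reason need be given, and that these people are outside the tolerability results.
- **Serious events may be covered.** A reader might infer that pre-randomisation SAEs are excluded outright. Section 10.2 has its own reporting rule with no start point, so the text is ambiguous and not a firm exclusion. This stands, and the ambiguity is itself worth removing.
- **The kit is a moulding tool, not the randomised SP1 treatment.** It is worn for two nights before allocation, and pooling its reactions with those of the SP1 or SP2 periods would blur the within-patient comparison. This stands as a reason for separate tabulation, but not for leaving the reactions unrecorded.
- **Selection is part of the design.** A reader might infer that tolerability results are tilted towards the self-moulded devices, since participants must get through SP1-type wear but only measurement for the bespoke device before randomisation. The order of steps permits this, but nothing in the documents shows that it happens or how large it would be. A participant for whom an SP2 cannot be made cannot enter a four-treatment crossover, and moving the AE start date does not change who is randomised.
- **Exposure is short and other traces exist.** Support calls are documented and the protocol expects a modest AE profile. This limits the importance of the gap. But those calls are logged to measure support needs, without AE grading or follow-up.

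**Conclusion.** The gap is real but limited. Section 3.4 requires two nights of wearing an SP1-type mould before randomisation, and section 10.1 opens AE recording only at randomisation. Reactions in between meet the protocol's AE definition but have no AE recording route, and the position of SAEs is ambiguous between sections 10.1 and 10.2. Participants who stop at this step are traceable through the screening log or a withdrawal CRF, but do not enter the tolerability results.

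It affects every randomised participant for at least two nights (180 to 192 participant-nights in total), plus an unknown number who are never randomised. No reaction or drop-out rate can be derived from the documents. Any percentage would be an assumption, and applying it to the 90 to 96 randomised would use the wrong denominator for people who stop before randomisation. The primary AHI comparison, the randomised within-patient device comparisons and the sample size are unaffected.

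The conclusion assumes that the kit counts as part of the trial intervention, as its place in the SP2 description indicates, and that the impression step is completed as written.

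**What to change.** - Amend section 10.1 so that the AE/SAE reporting period opens at consent or at issue of the impression kit, and state the same start point in section 10.2.
- Record reactions during the impression step on the existing AE form. As the participation number is assigned only at randomisation, use a screening identifier until then.
- Tabulate these reactions separately, labelled as arising from the impression mould, and keep them out of the randomised SP1 and SP2 summaries.
- In the participant flow, report impression failures and intolerance with all kit recipients as the denominator.

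The cost is a wording amendment and some extra recording on existing forms between kit issue and randomisation. The protocol does not state that interval; a few weeks is a reasonable expectation, given bespoke-device measurement about 1–2 weeks after baseline. No visit, sample-size or analysis-model change is needed.

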10.2 Serious Adverse Event Reporting

A Serious Adverse Event (SAE) is an AE which meets at least one of the following criteria:

- 1. Results in death
- 2. Is life-threatening (i.e. with an immediate risk of death at the time of the event)
- 3. Requires hospitalisation or prolongs existing hospitalisation (hospitalisation for elective treatment of a pre-existing condition is not included)
- 4. Results in persistent or significant disability or incapacity
- 5. Is a congenital abnormality or birth defect
- 6. Is considered to be an important medical event. This, though not included in the above, may jeopardise the patient and may require medical or surgical intervention to prevent one of the outcomes listed. Medical and scientific judgement should be exercised in deciding whether an AE is serious in other situations.

Serious Adverse Event Reporting

All SAEs should be reported to the sponsor within the specified timeline of a member of the trial team becoming aware of the event. SAEs which are Related and Unexpected (ie SUSARS – Suspected Unexpected Serious Adverse Reactions) will also be reported to the REC, within the appropriate time period. SUSARs will also be reported to Meditas or the PI at Addenbrooke's Maxillofacial Lab depending on the device in question.

All AEs should be reported to Meditas and the PI at Addenbrooke's Maxillofacial Lab (as relevant) within 3 months of the end of study.

Follow-up after Serious Adverse Events

All SAEs will be followed up until resolution or the event is considered stable.

11. Financial and Insurance

This study is being funding by the NIHR Health Technology Assessment (HTA) Programme. Any negligent harm to study participants will be covered by the NHS indemnity insurance.

12. Publication Policy

Any formal presentation or publication of data from this trial will be considered as a joint publication by the investigator(s) and the NIHR HTA Programme. Authorship will be determined by mutual agreement. All publications will acknowledge the funding body of the study. The data will be analysed, as stipulated in the protocol, by the Trust statisticians.

13. Amendments

All amendments will be discussed and approved by the Trial Steering Committee (TSC) before submission to the HTA, REC and R&D. No changes will be implemented before approval is given.

REFERENCES

APPENDIX 1: SUMMARY OF PREVIOUS STUDIES

The evidence supporting the treatment recommendations for mild to moderate OSAH were carefully reviewed in the preparation of the study.

CPAP vs. Control: As shown in Table 1, meta-analysis of up to 23 studies indicates a statistically significant benefit of CPAP compared to control in terms of both AHI [1] and ESS [1,2] although there was considerable statistical heterogeneity ($I^2 = 70.6\%$). Treatment effects were generally higher in severe baseline AHI and ESS subgroups and were smaller and more likely to be statistically non-significant in lower baseline AHI and ESS subgroups.

Study and Outcome/Subgroup Outcome	No. Studies	Mean Difference	95% Confidence Interval
Giles et al [1]			
AHI [PG/1st arm X studies] – Overall	7	-17.02	-19.25, -14.80
AHI [X studies] – Overall	1	-9.20	-18.26, -0.14
ESS [PG/1 st arm X studies] – Overall	10	-3.83	-4.57, -3.09
ESS [PG/1 st arm X studies] – Mild (=10) baseline ESS</td 2	-1.21	-2.98, 0.55	2	-1.21	-2.98, 0.55
ESS [PG/1 st arm X studies] – Mod (12-13.9) baseline ESS	2	-3.39	-4.81, -1.96
ESS [PG/1 st arm X studies] – Mod/Severe (14-15.9) baseline ESS	3	-5.36	-5.00, -3.71
ESS [PG/1 st arm X studies] – Severe (>/=16) baseline ESS	3	-4.61	-5.86, -3.35
ESS [PG/1 st arm X studies] – Mod [†] (15.1-29.9) baseline AHI	2	-2.45	-4.01, -0.90
ESS [PG/1 st arm X studies] – Severe [†] (>30) baseline AHI	7	-4.07	-5.03, -3.11
ESS [PG/1 st arm X studies] – Unclear baseline AHI	1	-4.80	-6.56, -3.04
ESS [X studies] – Overall	7	-1.92	-2.59, -1.25
ESS [X studies] – Mild (=10) baseline ESS</td 1	0.02	-3.51, 3.71	1	0.02	-3.51, 3.71
ESS [X studies] – Mild/Mod (10-11.9) baseline ESS	3	-1.34	-2.25, -0.42
ESS [X studies] – Mod (12-13.9) baseline ESS	3	-2.83	-3.86, -1.79
ESS [X studies] – Mild [†] (5-15) baseline AHI	3	-1.69	-3.18, -0.21
ESS [X studies] – Mod [†] (15.1-29.9) baseline AHI	3	-1.71	-2.49, -0.92
ESS [X studies] – Severe [†] (>30) baseline AHI	1	-6.01	-7.00, -3.00
McDaid et al [2]			
ESS [X studies] – Overall	23	-2.70	-3.45, -1.96
ESS [X studies] – Mild (0-9) baseline ESS	2	-1.07	-1.82, -0.31
ESS [X studies] – Mod (10-15) baseline ESS	16	-2.33	-3.04, -1.62
ESS [X studies] – Severe (16-24) baseline ESS	5	-4.99	-6.51, -3.47
ESS [X studies] – Mild (5-14) baseline AHI	3	-1.50	-3.43, 0.42
ESS [X studies] – Mod (15-30) baseline AHI	7	-2.04	-2.99, -1.09
ESS [X studies] – Severe (>30) baseline AHI	13	-3.41	-4.56, -2.26

Control= Sham (placebo) CPAP, placebo medication or best supportive care (including lifestyle modification); [PG/1st arm X studies] = Parallel group studies/First arm crossover studies; [X studies] = Crossover studies; †= AASM [3].

Table 1. CPAP versus Control: Apnoea Hypopnoea Index and Epworth Sleepiness Score

CPAP vs. MAD: Table 2 illustrates that these reviews found that CPAP significantly improved AHI compared to MAD [1] although in terms of ESS CPAP was not significantly different to MAD [1,2]. Subgroup/sensitivity analyses were consistent with this finding and the difference in ESS was greater in the severe than in the moderate baseline AHI subgroup. All studies were judged as moderate baseline sleepiness (ESS).

-

¹ Giles et al [1]) define control as sham CPAP, or other controls such as tablets, weight reduction or other preventative measures. McDaid et al [2] define control as placebo (including placebo pill or sham CPAP), or best supportive/usual care (including conservative intervention such as lifestyle advice regarding weight loss, alcohol consumption and sleep hygiene in addition to sleep posture advice or treatment).

Study and Outcome/Subgroup Outcome	No. Studies	Mean Difference	95% Confidence Interval
Giles et al [1]			
AHI [PG/1st arm X studies] – Overall	2	-13.02	-18.37, -7.67
AHI [X studies] – Overall	7	-7.97	-9.56, -6.38
ESS [PG/1 st arm X studies] – Overall	1	0.20	-1.60, 2.00
ESS [X studies] – Overall	4	-0.54	-1.38, 0.29
McDaid et al [2]			
ESS [X studies] – Overall { Mod (10- 15) baseline ESS}	6	-0.85	-2.11, 0.41
ESS [PG/1 st arm X studies] – Overall	2	-0.60	-2.70, 1.50
ESS [X studies] – Overall	4	-1.00	-1.10, 0.70
ESS [X studies] – Mod (15-30) baseline AHI	4	-0.20	-1.10, 0.70
ESS [X studies] – Severe (>30) baseline AHI	2	-1.80	-6.00, 2.30

[PG/1st arm X studies] = Parallel group studies/First arm crossover studies; [X studies] = Crossover studies.

Table 2. CPAP versus MAD: Apnoea Hypopnoea Index and Epworth Sleepiness Score

Our notion that the level of MAD sophistication might influence treatment outcome was partially supported. Censoring trials involving one-piece MADs (ESS [3 trials] 0.13, 95% CI: -0.71 to 0.97) and considering only two-piece MADs allowing incremental mandibular advancement (ESS [2 trials] 0.11, 95% CI: -0.84 to 1.06) in post-hoc sensitivity analyses [1] moved the effect in favour of MADs. In addition, compared to MAD CPAP significantly improved minimum saturation, arousals and sleep efficiency although there were no significant differences in objective sleepiness (Maintenance of Wakefulness Test) and generic or disease-specific HRQoL. Furthermore, although participants were significantly more likely to dropout on MAD than CPAP, despite mostly similar side effects, those who responded to both treatments preferred MAD [4,5].

MAD vs. sham-MAD: Lim et al [6] concluded that relative to a sham appliance, using a MAD resulted in significant benefits in AHI, ESS, arousals and minimum oxygen saturation (Table 3) but not in withdrawals or blood pressure. Although beneficial effects were found for HRQoL (Functional Outcomes of Sleep Questionnaire: weighted mean difference 17.00, 95% CI: 2.66 to 31.34), this was from a single small study.

Study and Outcome/Subgroup Outcome	No. Studies	Mean Difference	95% Confidence Interval
Lim et al (6)			
AHI [PG/1 st arm X studies]	5	-10.78	-15.53, -6.03
AHI [X studies]	4	-15.15	-19.40, -10.89
ESS [PG/1 st arm X studies]	4	-2.09	-3.80, -0.37
ESS [X studies]	4	-1.81	-2.72, -0.90

[PG/1st arm X studies] = Parallel group studies/First arm crossover studies; [X studies] = Crossover studies.

Table 3. MAD versus Sham MAD: Apnoea Hypopnoea Index and Epworth Sleepiness Score

[figure not shown]
REFERENCES

